Compression Wraps as adjuvant therapy in the management of acute systolic heart failure (CATAS-HF trial)

8/1/2020

- Study Protocol &
Statistical Analysis Plan

NCT# NCT04095416

STUDY TITLE: Compression wraps as adjuvant therapy in the management of acute systolic heart failure (CATAS-HF)**• STUDY AIM, BACKGROUND, AND DESIGN ABSTRACT**

Our goal is to measure the application of lower extremity compression wrapping as adjuvant therapy to diuresis in the management of patients hospitalized for acute systolic heart failure. Use of compression wrapping will be assessed through randomized parallel intervention clinical trial of patients admitted to Henry Ford Hospital I5 Cardiology service for management of acute systolic heart failure presenting with lower extremity edema. Enrolled patients will be managed with standard medical therapy, with (intervention) or without (control) the adjuvant use of lower extremity compression wrapping. Efficacy of the intervention will be analyzed for the following primary endpoints: 1) Percentage difference in weight before and after diuresis 2) Percent difference in Brain natriuretic peptide (BNP) from admission to discharge; 3) Difference in length of admission in days. Our hypothesis is adjuvant use of lower extremity compression wraps to standard medical therapy increases percentage of weight reduction achieved with diuresis, increases percent reduction in BNP after diuresis, and decreases total length of stay for patients hospitalized with acute systolic heart failure.

Lower extremity compression wraps are a low cost inpatient intervention when managing fluid overload in patients hospitalized for acute systolic heart failure, and presenting with lower extremity edema. Also, compression stockings are mainstay devices in the outpatient setting for improving symptoms of lower extremity edema in chronic systolic heart failure. However, the utility of compression wraps in managing patients hospitalized for acute systolic heart failure, and transitioning to the use of compression stockings for symptom management upon discharge, has not been thoroughly assessed. Current practice suggests use of lower extremity compression wraps can facilitate intravenous diuresis while inpatient, achieve more optimal discharge dry weight, and lower BNP levels prior to discharge. Demonstrating efficacy of such a low-cost, low-risk intervention in decreasing hospital stay and achieving more favorable patient outcomes will have considerable impact on standard practice.

• SUBJECT POPULATION AND ELIGIBILITY

Inclusion criteria: patients age greater than 18 and less than 85 years of age, admitted to I5 with Acute Systolic Heart Failure, and an ejection fraction of less than 50% as determined by echocardiogram within 6 months, requiring inpatient management with intravenous diuretic therapy. Must have a diagnosis of acute systolic heart failure (by ICD coding) on admission, of any underlying etiology. Must have documentation of pitting edema on primary assessment.

Exclusion criteria: patients who do not meet inclusion criteria, who cannot tolerate IV diuresis, who cannot wear or tolerate lower extremity compression stockings or wraps; active diagnosis of ESRD on dialysis or peripheral neuropathy; ejection fraction greater than 50% as evaluated by echocardiogram within 6 months.

Control population: Patients meeting inclusion criteria, managed on I5 for acute systolic heart failure with standard medical therapy without the use of lower extremity compression wraps.

This will allow direct comparison of the effect of intervention (lower extremity compression wraps) on the previously listed endpoints on the same patient population.

Since this study evaluates an already established component of standard medical practice, there will be no discrimination of patient populations in enrollment outside of the inclusion and exclusion criteria.

Patients will be enrolled exclusively based on inclusion and exclusion criteria, undergoing randomization into intervention or control groups. No screening tools will be used.

• STUDY PROCEDURES

The study will be an internally funded, parallel-intervention clinical trial studying the use of lower extremity compression stockings as adjuvant therapy to standard medical care in management of patients admitted for acute systolic heart failure. There will be two arms, intervention and control. 120 patients will be enrolled in the study, 60 to each arm, to achieve power above 80% with an alpha of 0.05, measuring continuous primary endpoints of average percent reduction in weight after diuresis, average change in BNP from admission to discharge, and average length of admission in days.

Data will be collected by Henry Ford personnel, for 120 patients previously admitted after January 2018 and managed on the HF Main cardiology I5 floor meeting inclusion criteria and managed with standard medical therapy without the use of compression stockings, and will undergo review by research team for enrollment into the control group. If additional patients are needed to achieve enrollment number of 60 control subjects, patients will be enrolled and randomized prospectively by the research team. Data collected retrospectively will be performed through Epic health medical record and charted on Excel spreadsheet, and will include admission length of stay, daily weights, daily urine outputs, daily diuretic dose and type(s) used, admission BNP, and discharge BNP. Research team will also perform chart review on enrolled patients to evaluate for 30-day readmission rate.

The intervention arm will include patients enrolled and randomized by the research team meeting inclusion criteria, and managed on HF Main cardiology I5 floor. This population will receive bilateral lower extremity compression wraps (ACE bandages) on day 1 of admission in addition to standard medical therapy. Data will be collected by the research team through Epic health medical record and will be charted on Excel spreadsheet, and will include admission length of stay, daily weights, daily urine outputs, daily diuretic dose and type(s) used, admission BNP, and discharge BNP. These charts will also undergo review by research team to evaluate for 30-day readmission rate.

Co-investigators will be responsible for retrospective and prospective data review for control population. Both co-investigators and sub-investigators will be responsible for enrolling patients in the study and collecting above mentioned data points. Nursing staff on the floor will undergo teaching on application of ACE compression wraps, and will be responsible for capturing physician order for wrap application and executing order, which will mark the beginning of the trial enrollment.

Data analysis will be conducted through the Division of Biostatistics and Research Epidemiology and will include descriptive statistics and univariate comparisons between treatment groups. T-test and ANOVA with post-hoc analysis will be used to evaluate for difference in the means of each endpoint previously listed for each treatment group. Patient information will be de-

identified prior to data analysis. Data for enrolled patients will be saved on secure Henry Ford Health System servers on Microsoft OneDrive cloud servers and shared among research team. Identifiers will include MRNs to access patient charts, collect and verify data, and perform review for 30-day readmission rates. Data will be stored for the entirety of the study, and promptly discarded in accordance with HFHS regulation at the completion of the study tentatively scheduled for January 2021. Data collected on patients excluded from the study will be discarded at the time of exclusion in accordance with HFHS regulation. Missing or incomplete data will prompt withdrawal of particular patient from study, and will factor into final data analysis as an intention to treat value.

Total time of subject enrollment in the study: duration of hospital stay. No additional visits or follow-up testing is required.

Literacy and language barrier concerns will be handled on a case-by-case basis, primarily using standard communication methods of translator services.

- **ANTICIPATED RISKS**

There are no significant anticipated risk beyond standard of care risk in management of patients with acute systolic heart failure. Intervention includes an already established therapy on patients with lower extremity edema. We are simply testing the formal efficacy of this intervention in an interventional study.

- **ANTICIPATED BENEFITS**

Anticipated benefits include: decreased length of stay, decreased amount of diuretic used, increased percentage of weight achieved through diuresis; greater percent of BNP reduction; decreased 30-day readmission rate.

- **RENUMERATION/COMPENSATION**

No compensation offered

- **COSTS**

There is no additional cost anticipated for this study outside of standard medical management of acute systolic heart failure and any additional medical conditions treated during the hospital admission.

- **ALTERNATIVES**

Intervention does not involve offering an established efficacious therapy to patients, and conversely control group is not being withheld from any known therapy that affects morbidity/mortality. No known alternatives.

- **CONSENT PROCESS AND DOCUMENTATION**

Co-investigators and sub-investigators enrolling patients will be responsible for obtaining consent from patients prior to enrollment. This will involve presentation of consent document with description of study. Patients will have the opportunity to privately ask questions and receive answers at the time of enrollment after the study is described to them in detail, including risks and benefits. There will be no duress or undue influence, as intervention is already a standard of medical practice. Patients will have the opportunity to refuse intervention. Patients will not be enrolled if they have diminished capacity or learning disability, or impairment of any kind. If patient is non-English speaking, consent form will be translated using standard translator services (in person translator, translator phone). Consent documentation will be stored on the Henry Ford secured OneDrive Microsoft cloud server. This information will only be accessible by research team. Information will be stored for the entirety of the study, and promptly discarded in accordance with HFHS regulation at the completion of the study tentatively scheduled for January 2020. Information collected on patients excluded from the study will be discarded at the time of exclusion in accordance with HFHS regulation.

- **WITHDRAWAL OF SUBJECTS**

Patients withdrawn from study will be notified, and information gathered from enrollment period will be analyzed as intention to treat. All information will be destroyed appropriately at the time of withdrawal.

- **PRIVACY AND CONFIDENTIALITY**

Patient information will be stored without identifiers. Access to patient chart will be provided to healthcare providers caring for patients during hospitalization, as well as co-investigators and PI of the study. Research team will then use a master key to remove identifiers. Data will be collected and pooled using this master key, and stored on secured HF servers under password protection for use by research team exclusively.

Important HIPAA Concerns

If you will be using, disclosing or accessing the health record (medical record, mental health or substance abuse records, etc) for research purposes, then HIPAA applies. If you are accessing medical records or PHI for screening purposes, HIPAA regulations apply and investigators will need to obtain prospective HIPAA authorization or apply for a waiver of HIPAA authorization for the screening activities, as applicable, depending on the nature of the study.

If accessing PHI for screening purposes and providing written authorization, describe how authorization will be obtained for the screening portion, who will obtain it or request and justification for a request for HIPAA waiver for recruitment purposes. If you are requesting waiver of HIPAA for screening purposes, describe the confidentiality procedures that will be used.

For more information on HIPAA authorization guidance, visit: <https://www.hhs.gov/hipaa/for-professionals/privacy/guidance/research/index.html>

NOTE: You may also need to obtain a waiver of documentation of informed consent (ie, signed consent) for screening purposes if you do not meet the requirements for waiving consent provided in the Consent Process section.

- **DATA AND SAFETY MONITORING PLAN**

PI and co-investigators will be directly involved in the enrollment of each subject. The intervention is low-risk and already a component of standard medical care. Nurses and sub-investigators will be allowed to care for enrolled patients under standard medical care. Each patient will be assessed at the start of enrollment, and at the end of hospitalization for compliance with standard medical care, as is the practice of all patients at Henry Ford Hospital. All adverse events and harm/near miss/sentinel events will be reported immediately to IRB. No such events are anticipated.

- **QUALIFICATIONS OF THE INVESTIGATOR(S)**

Principal Investigator, [name] is an ABMS certified physician in Cardiovascular Medicine, and Internal Medicine.

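### Controls are defined by non-use of compression with no time point, while wraps are fixed at day 1; on completed charts this favours shorter control stays, by an amount that depends on an unreported rate of later wrapping

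*Combined protocol and SAP*

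**What the plan says.** All references are to the combined protocol and SAP.

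- **Control definition.** SUBJECT POPULATION AND ELIGIBILITY describes controls as eligible patients "managed on I5 for acute systolic heart failure with standard medical therapy without the use of lower extremity compression wraps". This is treatment received. It gives no day on which non-use is judged and does not mention allocation.
- **Source of controls.** STUDY PROCEDURES collects data "for 120 patients previously admitted after January 2018", who were "managed with standard medical therapy without the use of compression stockings, and will undergo review by research team for enrollment into the control group". The word here is stockings, not wraps. Randomised controls are a top-up: "If additional patients are needed to achieve enrollment number of 60 control subjects, patients will be enrolled and randomized prospectively by the research team".
- **Intervention.** STUDY PROCEDURES gives the other arm "bilateral lower extremity compression wraps (ACE bandages) on day 1 of admission".
- **Background use.** The eligibility section gives this premise for its enrolment policy: "Since this study evaluates an already established component of standard medical practice". No rate, timing or reason for wrapping on I5 is reported.
- **Analysis.** STUDY PROCEDURES plans univariate comparisons of means by t-test and ANOVA. Length of admission is one of three primary endpoints.
- **Excluded patients.** "Data collected on patients excluded from the study will be discarded at the time of exclusion".

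**The concern.** The two arms are fixed at different times. A patient is in the intervention arm because of something done on day 1. A chart patient is a control because of something that did not happen over a stay that is already finished. If patients on I5 are sometimes first wrapped on a later day, screening charts for non-use removes them, and the chance of removal rises with every extra day in hospital. Control membership then depends on a post-baseline event tied to the endpoint.

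This needs no link between wrapping and prognosis; time at risk is enough. The result would be a control arm with too short a mean stay, which works against the trial's hypothesis and could hide a real benefit or suggest harm. The planned unadjusted comparison does not correct it. If data from rejected charts are discarded, its extent could not be examined afterwards.

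**Working it through.** **1. The plan's own figure.** The plan states 60 per arm for power above 80% at alpha 0.05, with no effect size or SD, so the power cannot be reproduced. Inverting the two-means formula (two-sided, normal approximation):

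d = (1.960 + 0.842) / √(60/2) = 2.802 / 5.477 = 0.511 SD.

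This difference is the yardstick for power in step 4.

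**2. Assumed inputs (none is in the documents).** Length of stay L is lognormal with mean 6 days and SD 4, rounded to whole days with a minimum of 1. Hence σ² = ln(1 + (4/6)²) = 0.368 and μ = ln 6 − 0.368/2 = 1.608; after rounding the SD is 4.01. Each day from day 2 carries a constant chance p of a first wrap, unrelated to prognosis. Wraps have no effect.

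**3. Selection.** A chart is kept only if never wrapped: P(kept | L) = (1 − p)^(L−1). The mean stay of kept controls is Σ L·f(L)·(1 − p)^(L−1) / Σ f(L)·(1 − p)^(L−1), where f(L) is the probability of a stay of L days. The standard error of a 60 v 60 difference is √(2 × 4.01² / 60) = 0.73 days.

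| p per day | Removed | Mean stay of those removed | Mean stay of those kept | Shift (days) | Shift in SE |
|---|---|---|---|---|---|
| 1% | 5% | 9.0 | 5.85 | −0.15 | 0.2 |
| 2% | 9% | 8.9 | 5.70 | −0.30 | 0.4 |
| 5% | 21% | 8.5 | 5.32 | −0.68 | 0.9 |
| 10% | 37% | 8.0 | 4.82 | −1.18 | 1.6 |

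**4. Consequences for the test.** Kept controls are also less variable, so the standard error falls slightly (to 0.67 days at p = 5%). With no true effect, the chance of wrongly finding that wraps lengthen stay is Φ(−1.96 + shift/SE), taking the shift as a positive number. At p = 5% this is Φ(−1.96 + 0.68/0.67) = 17%. For p = 1%, 2%, 5% and 10% it is 4%, 6%, 17% and 46%, against 2.5% nominal. Power for a true benefit of 0.511 SD falls from 80% to 75%, 70%, 54% and 28%.

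**5. Sensitivity.** With mean 5 and SD 3, the shift at p = 1% is −0.09 days. With mean 8 and SD 5, the shift at p = 10% is −1.77 days. These are the extremes of the scenarios examined; the direction is the same in all of them.

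**6. Cost of keeping later-wrapped controls.** Take mean 6, SD 4 and p = 5%. If a late wrap cut the remaining stay by 20% or 40%, the control mean would be 5.85 or 5.70 days instead of 6.00, a dilution of 0.15 or 0.30 days. Dropping those patients moves it to 5.32, a shift of 0.68 days, and does so even when wraps do nothing.

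**The case against.** The strongest reply is that the plan never says a control must be unwrapped at every point in the stay. It omits a time point, and similar with/without wording is used in the design abstract simply to describe the two arms. That is correct: whole-stay non-use is a reading. It remains the natural one for a completed chart judged on how the admission was managed, because nothing limits the judgement to day 1.

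Second, the chart criterion names stockings and the general definition names wraps. Read literally, a chart with ACE wraps but no stockings might be kept. STUDY PROCEDURES also calls the intervention stockings, so the terms may be interchangeable, but rejection of a wrapped chart is not certain until the wordings are reconciled.

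Third, later wrapping is assumed. The plan calls wraps established practice, yet it also says floor nurses will be taught to apply them, which suggests that use on I5 may not have been routine. This stands: the mechanism is sound but its size is unknown.

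Fourth, a reader might infer that randomised top-up controls who are wrapped later are dropped and their data destroyed, contrary to the intention-to-treat wording. The documents do not support this. Those patients are controls by allocation, the sentence on discarding data does not mention later wrapping, and withdrawn patients are said to be analysed as intention to treat. What is missing for them is a rule, not a correct one that is contradicted.

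Finally, the non-concurrent control arm is a larger issue, and its other differences could act either way. That is true, but they cannot be relied on to cancel this one.

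**Conclusion.** The concern holds as a conditional bias in the chart-derived controls. Selecting completed admissions on non-use of compression, against an intervention fixed at day 1, pushes control length of stay downward and so works against wraps. Under the stated assumptions the shift runs from about −0.15 days (0.2 standard errors) at 1% wrapped per day to −1.18 days (1.6 standard errors) at 10%. The upper end requires 37% of potential controls to be removed for wrapping; if later wrapping is rare, the bias is negligible.

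A reader might also infer that retained controls respond better on weight and BNP. The documents do not support that: shorter stays also mean fewer days of diuresis, so the direction for those endpoints is unknown. A link between later wrapping and persistent edema is likewise conjecture, and the length-of-stay result does not need it. The change should be made because it is inexpensive and the unknown rate could matter for a primary endpoint.

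**What to change.** 1. Reconcile wraps and stockings between SUBJECT POPULATION AND ELIGIBILITY and STUDY PROCEDURES, so that one term or an explicit list defines compression.
2. Define chart controls as eligible admissions with no compression on day 1, and keep them in the primary analysis if compression starts later.
3. State that prospectively randomised controls are analysed as allocated, whether or not they are later wrapped.
4. Record the date of first compression in both arms where Epic documents it, and report how many controls were later wrapped.
5. Use the never-wrapped comparison as a sensitivity analysis only, reporting the number it drops and their length of stay. Retain these de-identified fields long enough to do so.

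The cost is a reworded definition and one added data field. The contrast is somewhat diluted if wraps work, and historical wrap dates may be incompletely charted, since compression is not in the retrospective data list. The day-1 definition removes this post-baseline selection; it does not make past and current patients comparable in other respects.

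### If clearly more than 60 past patients qualify, no rule says which 60 become controls, and the exclusions need not be settled before the primary outcomes are seen

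*Combined protocol and SAP*

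**What the plan says.** All references are to the combined protocol and SAP.

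- **Target.** STUDY PROCEDURES: "120 patients will be enrolled in the study, 60 to each arm".
- **Pool.** Same section: "Data will be collected by Henry Ford personnel, for 120 patients previously admitted after January 2018". These patients were managed on the I5 floor without compression stockings and are described as meeting the inclusion criteria.
- **Step from pool to arm.** They "will undergo review by research team for enrollment into the control group".
- **Shortfall rule.** "If additional patients are needed to achieve enrollment number of 60 control subjects", further patients are enrolled and randomised prospectively. No counterpart covers a surplus.
- **Fields extracted.** "Data collected retrospectively will be performed through Epic health medical record and charted on Excel spreadsheet, and will include admission length of stay"; the list continues with daily weights and with BNP at admission and discharge. These supply all three primary endpoints in the abstract.
- **Who does it.** STUDY PROCEDURES gives co-investigators the data review for controls. Co-investigators and sub-investigators both enrol patients and collect the data.
- **Limits on selection.** SUBJECT POPULATION AND ELIGIBILITY: "Patients will be enrolled exclusively based on inclusion and exclusion criteria" and "there will be no discrimination of patient populations in enrollment outside of the inclusion and exclusion criteria".
- **Excluded patients.** STUDY PROCEDURES has data on excluded patients discarded when they are excluded, so collection may come before exclusion. De-identification is required only before analysis.

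**The concern.** A prospective control has no outcome when enrolled. A past patient's length of stay, weight loss and BNP change are already in the chart. The usual protection is to fix who is in the comparison group before anyone reads those fields, and this plan has no such step. It collects data on twice as many past patients as there are control places, then hands the choice to a team review whose order and method are not described.

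Even mild, unintended favouring of charts with slower weight loss or longer stays would shift the control mean and make wraps look effective. The planned t-tests and ANOVA are univariate comparisons and would not correct the shift. Because data on excluded patients are discarded and no screening log is required, a reader might also be unable to see why a chart was left out.

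**Working it through.** **1. Do the eligibility sentences fill the gap?** They state who may be a control. If 80 or 100 charts satisfy every criterion, they do not say which 60 enter. The plan gives no date order, random draw or matching.

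**2. Can a surplus arise?** The 120 are described as already meeting the inclusion criteria. The exclusions (dialysis, neuropathy, intolerance of IV diuresis or of compression) and incomplete data stand between 120 and 60. The documents do not say how many survive, so the number qualifying, N, is an assumption.

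**3. The plan's own figure.** The 60 per arm cannot be reproduced, because no effect size or SD is given. Back-solving for 80% power at two-sided 0.05 (the plan does not state sidedness):

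(1.960 + 0.842) × √(2/60) = 2.802 × 0.1826 = 0.51 SD.

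This serves only as a yardstick.

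**4. Possible size of the bias.** Assumptions: one normally distributed endpoint, no true effect, 60 wrap patients, and the 60 of N charts ranking highest on a score that has correlation r with the outcome. Neither r nor N is in the documents.

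- Control mean shift in SD: r × φ(z)/p, with p = 60/N and z the normal point with upper tail p.
- Shift in the test statistic: λ = shift × √(60/2) = shift × 5.477.
- Type I error: P(Z > 1.96 − λ) + P(Z < −1.96 − λ).

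At r = 0.2:

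| N qualifying | φ(z)/p | Shift (SD) | λ | Type I error |
|---|---|---|---|---|
| 120 | 0.798 | 0.160 | 0.874 | 0.139 + 0.002 = 14.1% |
| 100 | 0.644 | 0.129 | 0.705 | 0.105 + 0.004 = 10.9% |
| 80 | 0.424 | 0.085 | 0.464 | 0.067 + 0.008 = 7.5% |
| 70 | 0.263 | 0.053 | 0.288 | 0.047 + 0.012 = 6.0% |

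Simulation with the pooled t-test (300,000 runs per cell) gives 14.1%, 10.9% and 7.6% for N = 120, 100 and 80. For N = 70, a simulation of 200,000 runs gives 5.8%.

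**5. Sensitivity to r (simulated type I error).**

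| N | r = 0 | r = 0.1 | r = 0.2 | r = 0.3 |
|---|---|---|---|---|
| 120 | 4.9% | 7.1% | 14.1% | 26.1% |
| 100 | 5.0% | 6.4% | 10.9% | 18.4% |
| 80 | 5.0% | 5.6% | 7.6% | 10.8% |
| 70 | 5.0% | 5.2% | 5.8% | 7.2% |

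At r = 0.3 and N = 120 the shift is 0.24 SD, nearly half the 0.51 SD yardstick (0.24/0.51 = 0.47). With a rule unrelated to outcome (r = 0), the error stays at 5% whatever the surplus.

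**The case against.** **The plan already bars selection outside the criteria.** This stands in part. Choosing on outcome would breach the plan, and nothing suggests that it is intended. But the sentences set no procedure and cannot choose among charts that all qualify.

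**Most eligibility is settled by how the pool is defined.** This largely stands. On the plan's wording, the inclusion criteria and management without stockings define the 120. The exclusions are what clearly remain, and the point is limited to them and to the choice among a surplus. One of them, "who cannot wear or tolerate lower extremity compression stockings or wraps", is hard to judge in someone who was managed without compression.

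**There may be no surplus.** This stands as a condition. Collecting 120 may simply allow for attrition. CONSENT PROCESS AND DOCUMENTATION asks for consent before enrolment and states no exemption for chart controls; if it applies to them, the pool shrinks further. With 70 qualifying, the effect is small at the correlations shown.

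**The magnitude has no anchor in the documents.** This stands. Both r and N are assumed, and keeping the strict top 60 is the extreme form of selection at a given r.

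**Withdrawal as a second way to trim the controls.** A reader might infer that withdrawal for missing data also lets controls be removed on outcome. The documents do not support that. STUDY PROCEDURES and WITHDRAWAL OF SUBJECTS both say that withdrawn patients are analysed as intention to treat, and the latter has them notified, which suits prospective patients. That section also has their information destroyed. The conflict is a separate point.

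**Conclusion.** The point holds as a conditional gap. If clearly more than 60 past patients survive the exclusions, the plan allows the control arm to be chosen with all three primary outcomes visible, by staff who both enrol and collect data. At an assumed correlation of 0.2 with strict top-60 selection, type I error per endpoint runs from about 6% (70 qualifying) to about 14% (120 qualifying). The highest figures need nearly all 120 to qualify.

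Two stronger readings should be resisted. The documents do not show that outcomes will drive selection; they lack a safeguard against it. Nor do they show that reasons for exclusion will be lost: they discard the data on excluded patients and are silent on a de-identified tally of reasons, so the reasons could be lost, no more.

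The change should be made, but the point ranks below the larger problem that chart controls are not randomised. It falls away if every control is randomised prospectively.

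**What to change.** If chart controls are kept, amend STUDY PROCEDURES as follows:

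1. List all consecutive I5 admissions with the qualifying ICD code between a fixed start date and a fixed closing date.
2. Decide and lock eligibility, including every exclusion, before length of stay, weights and discharge BNP are extracted. Name in advance the chart entries that count for the tolerance exclusions.
3. If more than 60 qualify, take 60 by a prespecified outcome-neutral rule, such as the consecutive admissions nearest the closing date or a seeded random draw. Do not drop or replace a locked chart because of its outcome values or because an outcome is missing. If fewer than 60 qualify, the existing prospective route applies.
4. Keep a de-identified log of every reviewed chart with the reason for any exclusion, and amend the sentence in STUDY PROCEDURES on discarding excluded patients' data to allow it.

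The cost is wording, a changed order of extraction, slightly more chart work and a short log. The 60 per arm is unchanged. Concealment may be incomplete, because checking compression use or tolerance of IV diuresis means reading the hospital course, which may hint at length of stay. None of this turns past patients into randomised controls.
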